## **RISK AND BENEFIT OF THE STUDY PROTOCOL**

The study involves risks of possible adverse events related to the pharmacological therapies administered and the interventional procedure performed, which, however, are addressed in an expert and high-volume center (e.g. risks related to coronary angiography procedure, OCT or acetylcholine provocative test for patients randomized to “precision-medicine approach”, CMR, transesophageal echocardiography or transthoracic echocardiography with contrast medium, which however do not expose to ionizing radiation, venous blood draw which could lead to discomfort, pain or small bruises at the puncture site). However, with this prospectively designed trial, we have the opportunity to test the prognostic value of a targeted therapeutic approach based on the identification of the underlying cause. Of importance, the results deriving from our trial may open the way for a new pathophysiology-driven approach with cause-target therapies personalized for the mechanism of MINOCA. Therefore, we retain that the benefits of a precision-medicine approach for the treatment of MINOCA will outweigh all the possible risks associated with this clinical study”.

## **ETHICAL CONSIDERATIONS AND RESULTS SHARING**

The study will be conducted in 3 centers in Italy. The authorization by AIFA (OsSC), competent authority on the matter, the single opinion expressed by the coordinating center and the opinions expressed by the respective ethics committees of the clinical centers involved regarding the conduct

of the study will be transmitted, in writing and complete, in all their parts, to the Investigator before the start of the study.

## **24. Research Ethical Approval**

**Competent Ethical Committee (CEC):** The investigator/ PI responsible for each participating center ensures that the institutional ethics committee has provided a favorable opinion. No changes to the protocol will be made without the prior approval of the Investigator, authorization from AIFA (OsSC) and from the Ethics Committee of the coordinating center and subsequently by the other CECs of the centers involved, except when it is necessary to prevent apparently immediate risk to study participants. In this case, to prevent any serious risk for the patient, the modification to the protocol can be implemented immediately but at the same time submitted to AIFA (OsSC) and to the coordinating EC and to the other ECs involved. Premature interruption of the study must be reported within 15 days. The regular term of the study will be communicated to AIFA (OsSC) and the CEC within 90 days. The final study report will be reported within 1 year of the end of the study.

**Competent authorities:** The approval of the Italian Medicines Agency (AIFA-OsSC) will be obtained before the start of the clinical trial. Severe and unexpected adverse reactions (SAEs), related to the use of the study drugs, are subject to rapid reporting. They will be communicated to the competent authorities by the PI of the clinical site to the PI of the coordinating Clinical Center from the study (s) to the Minister of Health (CA) and to all CEs, where necessary. All other events will be reported in the annual safety report. The description and seriousness of the events, anticipated or not, the causal association and the dosage will be included in the report. Reactions to fatal or life-threatening drugs will be reported as soon as possible, but no later than 7 calendar days. All the others, however, no later than 15 calendar days. The regular term of the study will be reported to the authorities within 90 days and the final report submitted within 1 year of the end of the study.

**Ethical conduct of the study:** The study will be conducted in accordance with the protocol and principles set out in the latest available version of the Declaration of Helsinki, in the latest version available guidelines of Good Clinical practice (GCP) issued by the ICH, in the latest updates of national laws / regulations and respecting the dictates of the Italian competent authority. The CEC and regulatory authorities will receive periodic and annual safety reports and will be informed about the interruption / suspension of the study in accordance with local requirements.

## **25. Amendments to the Protocol**

The investigator ([name]) is authorized to make amendments to the protocol. The PIs of each site are allowed to make suggestions for any amendments. Important changes to the protocol (eg change of eligibility criteria, outcomes, statistical analysis) will be communicated within 5 days to the parties involved (investigators, competent authorities (AIFA-OsSC) and CEC, study participants, online registers, regulatory authorities). Substantial amendments will only be implemented after approval by the CEC and the competent authority. In emergency conditions, deviations from the protocol to protect the rights, safety and well-being of participants may be made without the prior approval of the sponsor or the CEC / CEA. Such deviations must be documented and promptly reported to the sponsor, AIFA-OsSC and the CEA. All non-substantial amendments will be communicated to AIFA-OsSC as soon as possible and to the CEC in the context of the Development Safety Update Report (DSUR).

## **26. Patient Information and Informed Consent and Consent to the Processing of Personal Data**

The PIs of each clinical site will explain to patients the nature of the study, its rationale, the procedures involved, the duration, the potential risks and benefits, and any possible inconvenience both orally and by means of a written form (Patient Information: Each patient will be informed about the voluntary participation in the study and the possibility, at any time, to withdraw from the study without incurring any deterioration in the quality of medical assistance and treatments. The patient's data will be anonymized after the withdrawal of informed consent and the patient will be informed about any alternative treatments. Patients should be informed that other authorized individuals, in addition to their doctor, may review their personal data and will issue a consent to the processing of personal data in this regard. All study participants will be provided with sufficient information to make an informed decision about participating in the study. They will be given the opportunity to discuss treatment options and participation in the study with relatives or other trusted persons. The patient information sheet, the consent form and the consent form for the processing of personal data will be submitted to the respective CEC and the competent authorities (OsSC) for review and approval. The participant's formal consent, accompanied by the appropriate approved forms, must be obtained before submitting the participant to any procedure. Participants should read and consider the information received before dating and signing the consent form and attached forms, a copy of which will be provided to them. The consent form and the attached forms will also be signed by the investigator (or his delegate) and will be kept in the official documents of the study.

## **27. Confidentiality and Data Protection**

Direct access to the SD will be guaranteed for the purposes of monitoring, audits and inspections.

The investigator supports and abides by the principle of the participant's right to privacy and compliance with privacy regulations. In particular, the anonymity of the participants will be guaranteed if data is presented at scientific meetings or if they are published in scientific journals.

The medical information obtained as a result of the study is to be considered confidential and its disclosure to third parties is prohibited. Confidentiality will be further guaranteed by the use of identification codes of the subjects to be matched to processing data in digital files.

For verification purposes, relevant agencies (AIFA-OsSC), or CECs may request access to parts of the clinical records relevant to the study, including the participants' medical history.

## **28. Conflicts of Interest**

Investigators participating in the study must ensure that they have no agreement or no economic interest, direct or indirect, with the manufacturers of the study drugs.

## **29. Audits and inspections**

Responsible ethics committees, sponsor and authorities have the right to inspect the practice and / or manufacturing sites at any time before, during and after clinical conduct. There will be no further audits beyond monitoring and inspections. The study documentation and Source Data (SD) will be accessible to auditors / inspectors (including CECs and CAs) and questions will be answered during the inspection. All parties involved must treat participant data as strictly confidential.

## **Insurance**

The promoter will be responsible for providing insurance coverage for the study for all the enrolling sites.

## **31. Publication Policy**

The steering committee and investigators undertake to publish and disseminate the study results. The PROMISE study is a multicenter, randomized study. All public submissions, manuscript generation and submission will be led by the PI, who will create and coordinate a publication committee. This study represents a shared effort between investigators and collaborators and, as such, the parties agree that any party's recommendations regarding the manuscript or text should be taken into account in preparing the final scientific paper for submission or publication. The final database will be kept at the University of Sacred Heart, Rome, which will not release data or material relevant to the study without the permission of the PI. All PIs will be on the list of co-authors on all abstracts

and publications. Therefore, their adherence to the publication is required. Publication and / or submissions based on single clinical site data are not permitted until the results of the multicenter study are published. All data from individual sites will need to be generated from the central database - local databases are not allowed. All proposals for publications and presentations deriving from or related to the study must be submitted to the Steering Committee for review and approval prior to submission for presentation or publication. The Steering Committee will receive the material of each submission / publication proposal prior to submission / submission, in time to be reviewed by all parties.

### **32. Informed consensus**

*See the files attached.*

All patients must date and sign informed consent first to enter the studio and before any activity related to experimentation.

In case of amendments that could directly affect the continued participation in the trial by the person, further consent must be obtained from the same.

### **33. Management of biological materials**

**Blood sample collection:** 42 mL venous blood samples will be collected at the time of coronary angiography or within 12 hours from coronary angiography. Biochemical profile for evaluating the expression of Endothelin-1 (ET-1) and Neuropeptide Y (NPY), C-Reactive Protein (CRP), soluble CD40 ligand (sCD40L) will be performed on plasma and serum samples at baseline with ELISA kit.

Peripheral blood mononuclear cells (PBMC) will be isolated from EDTA blood by density gradient centrifugation. Serum and PBMC expression levels for deregulated miRNAs will be performed on the same samples to test circulating levels of miR-16, miR-26a, miR-145, miR-222, miR-155-5p, miR-483-5p and miR-451a with Serum microRNA microarray commercial kit. Coded plasma, serum and PBMC samples will be stored at -80°C at FPG XBiogem Biobanc.

All experiments and analysis will be performed at the “Cellular and molecular cardiology laboratory” of the Department of Cardiovascular Science. Coded plasma, serum and PBMC sample from patients enrolled in the other centers (Centro Cardiologico Monzino IRCCS and IRCCS Policlinico San

Donato) will be collected with the same protocol for procedure standardization and will be shipped to our Unit.

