in patients with stable angina and non-obstructive CAD. Indeed, the landmark Coronary Microvascular Angina (CorMicA) trial showed that in these patients a strategy of adjunctive invasive testing for disorders of coronary function linked with stratified medical therapy led to improvement in patient outcomes, including reduction in angina severity and better quality of life. If a similar precision-medicine approach is effective also in patients with MINOCA has never been assessed. We previously demonstrated that patients with a positive provocative test for epicardial or microvascular spasm had a higher occurrence of future cardiac events, thus identifying high-risk MINOCA patients that may need a more aggressive therapy. Moreover, biochemical profile of MINOCA patients is still largely unknown and whatever exist a unique profile associated with specific pathophysiological mechanisms remains unknown. Endothelin-1 (ET-1) and neuropeptide Y (NPY) are endogenous vasoactive substances regulating coronary vasomotion involved in coronary spasm. On the other hand, elevated plasma levels of soluble CD40L and C-reactive protein (CRP) are involved in inflammatory activation during MI with plaque rupture. Moreover, also circulating miRNA may be associated with specific pathophysiological mechanisms of MINOCA, and may represent new promising diagnostic tools. Particularly, the up-regulation of miR-16 and miR-26a and the down-regulation of miR-1 and miR-133, have been reported to characterize coronary microvascular spasm, whereas, miR-145 and miR-222 may help in identifying patients with epicardial spasm. Finally, miR-155-5p, miR-483-5p and miR-451a have been suggested as novel biomarkers for the early identification of plaque rupture. However, miRNA assessment in MINOCA patients has never been performed. In the absence of dedicated randomized controlled trials, current guidelines do not specifically address the issue about acute and long-term management of patients with MINOCA. The effects of secondary preventive treatments proven beneficial in patients with MICAD are unknown in MINOCA patients. The "one-size-fits-all" approach used for MICAD treatment may not apply uniformly to all MINOCA patients, which instead should be "personalized" depending on the underlying pathophysiological mechanism responsible for the clinical presentation. Thus, the next key step in the management of MINOCA is to demonstrate the benefits of tailored therapies on cardiovascular and quality-of-life outcomes. With this prospectively designed trial, we have the opportunity to test the prognostic value of a targeted therapeutic approach based on the identification of the underlying cause. Of importance, the results deriving from our trial may open the way for a new pathophysiology-driven approach with cause-target therapies personalized for the mechanisms of MINOCA.

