### **11a. Intervention(s):**

Patients with myocardial infarction undergoing to clinically indicated coronary angiography will be asked to sign the informed consent to the study before the coronary angiography/ventriculography and enrolled only after MINOCA diagnosis. MINOCA patients will be then randomized 1:1 (using an online software available 24h/24h) to:

**A. "Precision medicine approach"** consisting of:

*Comprehensive diagnostic work-up with:*

- Coronary angiography and ventriculography in all patients
- OCT (if coronary plaque rupture/erosion is suspected) at the time of coronary angiography in the cath-lab.
- Acetylcholine provocative test (to assess the presence of coronary vasospasm) at the time of coronary angiography in the cath-lab.
- TE-Echo and/or CE-Echo (if distal/microvascular embolization is suspected) during the hospitalization at the echo laboratory
- Blood sampling for circulating biomarkers and miRNA expression profile at the time of coronary angiography or within 12 hours from coronary angiography. Blood sampling will be processed and analysed in the research laboratory of the Department of Cardiovascular Science. Biological aliquots will be preserved at XBiogem Biobank at Fondazione Policlinico Universitario A. Gemelli IRCCS, Rome.
- Trans-thoracic echocardiography in all patients during the index hospitalization
- CMR in all cases during the index hospitalization.

*Targeted pharmacological treatment specific for the underlying cause:*

- DAPT ± stent implantation (if required), statins, beta-blockers, ACEi/ARB (in case of evidence of plaque rupture/erosion)
- CCB and/or nitrates (in case of documentation of coronary vasospasm)
- Anticoagulation (in case of coronary embolism).

**B. "Standard approach"** consisting of:

*Routine diagnostic work-up with:*

- Coronary angiography and ventriculography
- Transthoracic echocardiography in all patients during the index hospitalization
- CMR with contrast media only if clinically indicated (i.e. to exclude myocarditis or takotsubo syndrome)

*Standard medical treatment with:*

- DAPT in all patients
- Beta-blockers (if indicated by the clinical context, i.e. documentation of left ventricular ejection fraction <50%, tachycardia).

- High intensity statins in all patients
- ACEi/ARB (if clinically indicated).

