Pharmacological strategy will be started after the coronary angiography during the index hospitalization. All the procedures will be done by cardiologists with experience in the specific field. All three enrolling centers already have a high proficiency in performing all the procedures required for this study.

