### **Interventional Procedures:**

- *Coronary angiography*: coronary angiography will be performed via the transradial or transfemoral approach with the use of a 6F sheath. Coronary angiography will be performed within 90 minutes from hospital admission in patients presenting with persistent ST-segment elevation, and within 48 hours in patients presenting with non-ST-segment elevation. Unfractionated heparin (initial weight-adjusted intravenous bolus of 60 IU/Kg, with repeat boluses to achieve an activated clotting time of 250 to 300 seconds) was administered in all patients. If evidence of plaque rupture
- *Percutaneous coronary intervention (PCI)*: PCI with stent implantation will be considered in selected cases with evidences of plaque rupture
- *OCT imaging*: OCT imaging will be performed in the culprit artery in all patients randomized to the “precision medicine approach” with angiographic aspect of complex atheromatous plaque suggestive of plaque rupture. A 0.014-inch guidewire will be placed distally in the target vessel and an intracoronary injection of 200 µg of nitroglycerine will be performed. Frequency domain OCT (FD-OCT) images are acquired by a commercially available system (C7 System, LightLab Imaging Inc/ St Jude Medical, Westford, MA) connected to an OCT catheter (C7 Dragonfly; LightLab Imaging Inc/ St Jude Medical, Westford, MA), which was advanced to the culprit lesion. The FD-OCT run will be performed using the integrated automated pullback device at 20 mm/s. During image acquisition, coronary blood flow will be replaced by continuous flushing of contrast media directly from the guiding catheter at a rate of 4 ml/s with a power injector in order to create a virtually blood-free environment. Plaque rupture will be defined by the presence of fibrous cap discontinuity with a clear communication between the lumen and inner core of a plaque or with a cavity formation within the plaque. Plaque erosion will be identified by the presence of attached thrombus overlying an intact and visualized plaque, luminal surface irregularity at the culprit lesion in

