the absence of thrombus, or attenuation of underlying plaque by thrombus without superficial lipid or calcification immediately proximal or distal to the site of thrombus. Considering that OCT does not provide an adequate resolution to identify the endothelial lining, the definition of plaque erosion should be considered a diagnosis of exclusion, requiring the absence of fibrous cap rupture. Thrombus will be defined as an irregular mass (diameter > 250 µm) either attached to the luminal surface or floating within the lumen.

- *TT-Echocardiography*: TT-Echo will be used to calculate left and right ventricular and atrial dimensions, left and right ventricular systolic function, transmitral flow Doppler spectra, mitral and tricuspidal valve annulus tissue Doppler spectra, ejection time and stroke volume, inferior vena cava, aorta and pulmonary artery diameters and Doppler spectra, according to the recommendations of the American Society of Echocardiography.
- *TE/contrast echocardiography*: In patients with angiographic evidence of distal microembolization, TE-Echo consisting of an echocardiographic probe inserted in to the oesophagus will be used to detect a hidden cardioembolic source (i.e. left atrial thrombus); in patients with suspected left ventricular source of cardioembolism, contrast echocardiography consisting of a 0.3ml solution of SONOVUE will be used.
- *Acetylcholine provocative test*: ACh will be administered in a stepwise manner into the left coronary artery (LCA) (20–200 µg) or into the right coronary artery (RCA) (20–50 µg) over a period of 3 min with a 2–3 min interval between injections. Coronary angiography will be performed 1 min after each injection of these agents and/or when chest pain and/or ischaemic ECG shifts were observed. The decision of testing with provocative test LCA or RCA as first will be left to the discretion of the physicians; both LCA and RCA will be tested if the first test was negative. Angiographic responses during the provocative test will be assessed in multiple orthogonal views in order to detect the most severe narrowing and/or analysed by using computerized quantitative coronary angiography (QCA-CMS, Version 6.0, Medis-Software, Leiden, The Netherlands).

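### The single baseline biomarker draw has no stated order relative to the acetylcholine test, OCT or the first cause-specific drug, so the plan permits confounding of the biomarker endpoint

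*Combined protocol and SAP*

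**What the plan says.** **The draw.** Section 33 says "42 mL venous blood samples will be collected at the time of coronary angiography or within 12 hours from coronary angiography". The arm A list in section 11a gives the same window ("Blood sampling for circulating biomarkers and miRNA expression profile at the time of coronary angiography or within 12 hours from coronary angiography"), and so do the circulating-biomarkers item under Interventional Procedures and the T0 list in section 13. The schedule table marks the draw at day 0 only. Section 33 says the assays "will be performed on plasma and serum samples at baseline with ELISA kit".

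**The tests.** Arm A lists "Acetylcholine provocative test (to assess the presence of coronary vasospasm) at the time of coronary angiography in the cath-lab". OCT is done in the same session, but only when plaque rupture or erosion is suspected, and is preceded by intracoronary nitroglycerine. For acetylcholine, "both LCA and RCA will be tested if the first test was negative".

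**The drugs.** "Pharmacological strategy will be started after the coronary angiography during the index hospitalization". No hour is given. In arm A the drugs depend on the cause found: DAPT, statins, beta-blockers and ACEi/ARB for plaque rupture or erosion; CCB and/or nitrates for vasospasm; anticoagulation for embolism.

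**The use.** Section 12 makes the markers' ability to diagnose and stratify specific causes a secondary endpoint. Section 20 contains no biomarker model and no adjustment for draw timing.

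**The concern.** The panel is meant to separate causes on the strength of one sample. For that, the sample should reflect the patient's state before anything is done that depends on the cause. The window does not secure this. Some patients may be sampled before provocation, OCT and treatment, and others hours afterwards.

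The exposures are not neutral with respect to the label being predicted. A positive acetylcholine test provokes spasm in the patients who will be labelled as spasm, and the protocol's rationale for two of the markers is that "Endothelin-1 (ET-1) and neuropeptide Y (NPY) are endogenous vasoactive substances regulating coronary vasomotion involved in coronary spasm". OCT and its nitroglycerine go to patients with suspected plaque rupture. The drugs are chosen by cause. If any of these moves a marker, a difference between cause groups could reflect the work-up or the treatment rather than the mechanism, or a genuine difference could be blunted.

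At stake is the interpretation of a named secondary objective and endpoint.

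**Working it through.** **1. The plan's own figure.** The only calculation in the plan is for the SAQ: difference 9, SD 19, two-sided 5%, power 80%. n = 2 × (1.960 + 0.842)² × 19² / 9² = 2 × 7.85 × 361 / 81 ≈ 70 per group. It reproduces and does not depend on blood-draw timing. There is no calculation for the biomarker endpoint.

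**2. Where the draw can fall.** The draw is listed only under arm A, which is about 180 / 2 = 90 patients. Randomisation follows immediately on the diagnostic angiogram (sections 16-17), so the draw comes after that angiogram. The tests belong to the same session. A draw taken in the session can precede or follow them; one taken later in the 12 hours follows them, and may also follow the first targeted dose.

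**3. What varies with cause.**
- Acetylcholine: listed for every arm A patient, so receipt does not vary. The provoked response does, and so does the extent, because the second artery is tested only after a negative first test.
- OCT and nitroglycerine: only where plaque rupture or erosion is suspected.
- Drugs: by cause, from an unstated time after angiography.
- Embolism work-up (TE-Echo and/or CE-Echo): at any time in the hospitalisation, so the interval between drug and draw can also differ by cause.

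**4. Illustration as AUC.** Assume a normally distributed marker with equal SD and no true difference between two causes, and a shift of d SD after exposure in one cause group only. Then AUC = Φ(d/√2) when all of that group's samples are post-exposure. When half are, the AUC is the average of that value and 0.50.

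| d (assumed) | all post-exposure | half post-exposure |
|---|---|---|
| 0.5 | Φ(0.354) = 0.638 | (0.50 + 0.638)/2 = 0.57 |
| 1.0 | Φ(0.707) = 0.760 | (0.50 + 0.760)/2 = 0.63 |

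If timing and shift are the same in both groups, the distributions coincide and the AUC stays at 0.50.

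**5. Illustration as false positives.** Two causes with 45 patients each, no true difference, two-sample t-test at 0.05, 20,000 simulated trials per scenario:

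| d (assumed) | same shift, 50% v 50% post-exposure | same shift, 70% v 30% | same shift, 90% v 10% | all post-exposure, only one cause shifts |
|---|---|---|---|---|
| 0.25 | 5% | 7.5% | 15% | 22% |
| 0.5 | 5% | 15% | 45% | 65% |
| 1.0 | 5% | 39% | 95% | above 99% |

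With 30 patients per cause the inflated rates are lower: at d = 0.5, for example, 12%, 33% and 48% in the last three columns.

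The shifts, timing splits and group sizes in steps 4 and 5 are assumptions; the documents supply none of them.

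**The case against.** The strongest reply is that confounding is possible here but not shown. No section says that acetylcholine, OCT, nitroglycerine or a few hours of any drug changes a listed marker in venous blood; the Introduction only associates markers with mechanisms. That stands, and the calculations illustrate a possibility rather than an expected effect. Small shifts with modest imbalance do little (7.5% against a nominal 5%), and balanced timing with a common shift does nothing.

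Several stronger readings are tempting, and the documents do not support them:
- *Acetylcholine exposure depends on cause.* Everyone in arm A is tested; only response and extent differ. Patients negative on the first test receive more testing, which could act against the effect of provoked spasm. The direction is not known.
- *Late samples are necessarily on cause-specific drugs.* The start hour is unstated, and the first targeted dose may follow the draw.
- *Time since admission confounds the causes.* Angiography is done "within 90 minutes from hospital admission in patients presenting with persistent ST-segment elevation, and within 48 hours in patients presenting with non-ST-segment elevation", so the draw can lie up to 1.5 + 12 = 13.5 h or 48 + 12 = 60 h after admission. That contrast is by ECG presentation. No section ties ST elevation to a cause, T0 records ST-segment features, and the documents give no marker kinetics, for CRP or any other.
- *The damage could never be repaired.* The documents do not require these times to be collected, but the eCRF is not shown. Section 18 requires catheterisation reports and laboratory results as source documents, from which some times may be recoverable.

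The reply does not answer the central point. Section 33 says the other centres follow the same collection protocol, but that protocol leaves the order open, and nothing in the plan makes timing comparable across causes.

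**Conclusion.** The point holds as a design weakness in one secondary endpoint, measured in one arm. The plan allows pre- and post-exposure samples to be mixed under the name of baseline, while the exposures vary with the cause being predicted. Confounding is therefore permitted, not demonstrated.

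Its size cannot be derived from the documents. The AUCs of 0.64 to 0.76 (all post-exposure) and about 0.57 to 0.63 (half post-exposure) rest on an assumed 0.5 to 1 SD shift confined to one cause group; with equal timing and equal shift the bias is nil. It would go too far to infer that the biomarker results will be uninterpretable. What follows is that, as written, the plan offers no protection against this explanation of a positive finding. The SAQ primary endpoint and its sample size are untouched. The change is worth making because it is cheap.

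**What to change.** - **Order.** In the arm A list of section 11a, the circulating-biomarkers item under Interventional Procedures, the T0 list in section 13, and section 33, set the standard draw after randomisation and before the acetylcholine test, OCT with nitroglycerine, and the first cause-specific dose. Keep the 12-hour window only as a fallback. This changes the sampling order, not any test, drug or dose.
- **Times.** Add eCRF fields for the times of blood draw, acetylcholine test, OCT, first targeted dose and symptom onset.
- **Analysis.** In section 20, pre-specify that the main biomarker analysis uses pre-exposure draws, with a sensitivity analysis of all samples adjusted for draw timing.

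**Cost.** Protocol and laboratory-manual wording and a few eCRF fields; the number of samples does not change. Consent is already signed before angiography, so an early draw is feasible. The real downside is that some of the roughly 90 arm A patients will have no pre-exposure sample and will leave the main biomarker analysis, possibly not at random (for instance out of hours, or in urgent ST-elevation cases). Their number and characteristics should be reported, and the all-sample analysis shows whether their exclusion matters.
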